1 PROTOCOL SUMMARY

1.1 SYNOPSIS

Title:

DEMONSTRATION OF AN ARTIFICIAL INTELLIGENCE BASED CLOSED LOOP GLUCOSE CONTROL SYSTEM AS A THERAPEUTIC MODALITY IN TYPE 1 AND TYPE 2 DIABETIC PATIENTS

Study Description:

Tight glucose control in the Intensive Care Unit (ICU) setting is difficult to achieve. We hypothesize that a closed loop glucose control system based on artificial intelligence (AI) will improve upon the glucose control currently achieved by open loop systems, and may improve the outcomes of critically ill patients, including those with COVID-19. This Early Feasibility Study (EFS) will test the ability of a prototype artificial intelligence based closed loop glucose control system named FUSION, to provide safe and effective glucose control in subjects with type 1 and type 2 diabetes in a clinical research center (CRC) setting. Subjects with type 1 diabetes have been chosen as they lack native Insulin production, which makes it

challenging to provide safe and effective glucose control for them. Subjects with type 2 diabetes have been chosen as they are insulin resistant, which makes their insulin resistance profiles like that of ICU patients. As this is a continuation of a first in human study of a new medical device, the controlled environment of the CRC is preferable to the less controlled environment of an ICU setting.

Objectives:

Primary Objectives:

1. The primary safety objective of this first in human study is to test the hypothesis that an AI based closed loop glucose control system will be able to safely control the blood glucose levels of participants with type 1 and type 2 diabetes during a 24 hour stay in the CRC setting.
2. The primary efficacy objective of this first in human study is to test the hypothesis that an AI based closed loop glucose control system will effectively control the blood glucose levels of participants with type 1 and type 2 diabetes during a 24 hour stay in the CRC setting.

Secondary Objectives:

The secondary objectives of this study are to test the hypothesis that an AI based glucose controller will be effective in minimizing glucose curve variations commonly observed in critically ill patients.

Endpoints:

Primary Endpoint:

1. The primary safety endpoint will be the percent of all glucose values that are within the glucose range of less than < 70 mg/dL. Time frame will be from start of use of AI controller until end of use of AI controller.

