2.3 STUDY RATIONALE – FUSION AI BASED ARTIFICIAL PANCREAS SYSTEM

The novel glucose control system to be tested in this study is an expert based rule system or Knowledge Based System.^{49,50} This system should be considered a form of artificial intelligence, whose main goal is to completely model the natural glucose homeostatic system. The essential elements of the native

glucoregulatory system, which were used to create the AI based system under study, have been reviewed⁵¹ by [name], who is the developer of the novel AI based glucose controller to be tested in this study. If successful, this controller could be utilized in a closed loop glucose control system (artificial pancreas) for treatment of dysglycemia in ICU patients.

Through an intensive review of how the native glucose control system functions (e.g., pancreas & liver), a knowledge based multiple input multiple output (MIMO) glucose control system has been developed.⁵² **The algorithms of this system use the four input variables of absolute glucose, glucose rate of change, weight based intravenous insulin dose and weight based intravenous dextrose dose.** Based on the values of these four input variables and the desired glucose control range, the two output variables of continuous intravenous insulin and continuous intravenous dextrose are adjusted. The results from the primary knowledge-based controller are also run through additional knowledge based controllers. These additional controllers monitor for outlying situations such as rapid falls or rise of blood glucose levels. These controllers will modify the two output variables from the primary controller if the clinical situation warrants such a change. Through utilization of the proper control techniques and frequent adjustment of the insulin and/or dextrose infusion rates (every 5 or 10 minutes), tight control of glucose will be achieved. In addition, episodes of clinically significant hypoglycemia will be avoided, and glucose variability will be minimized.

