8.1.1.5 VISIT 3, TIME 5 TO 29 HOURS (CLOSED LOOP GLUCOSE CONTROL SESSION)

The closed loop glucose control session will not begin until the following criteria has been met:

1. Both Dexcom G6 CGM's are returning glucose values and have been calibrated – if necessary; or replaced – if necessary.

Please refer to the below standard operating procedure (SOP) document for the calibration procedure for the Dexcom G6 CGM's, setting up the FUSION system, and initiating it's software:

FUSION System SOP

To better simulate how the FUSION system will be used in the ICU setting, no run-in period will be performed prior to the subject consuming the first meal. During the 24-hour closed loop glucose control study (time 5 to 29 hours), blood glucose control will be performed autonomously by Ideal Medical Technologies FUSION glucose control system. For safety reasons, the subjects will have a Reference Glucose Value independently measured every 10-60 minutes on the Nova StatStrip Hospital Glucose Meter System. These independent Reference Glucose Values will not be used by the FUSION system for glucose control. After 2-3 hours of confirmed CGM accuracy (e.g., from 0900 to 1200), the closed loop glucose control session will begin. The first meal consumed during the closed loop glucose control session will be lunch.

Lunch will consist of 60 grams of carbohydrate (45-60% of total meal Kcal's) and be consumed beginning at ~1200 hours (the beginning of the closed loop glucose control session). Dinner will consist of 75 grams of carbohydrates (45-60% of total meal Kcal's) and be consumed beginning at 1800 hours (6 hours after beginning of closed loop glucose control session). Breakfast will consist of 50 grams of carbohydrate (45-60% of total meal Kcal's) and be consumed beginning at 0800 hours on day 2 of the closed loop session began (20 hours after the beginning of the closed loop glucose control session).

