Subjects will be allowed to have snacks between the hours of 2100 on day 1 and 0600 hours on day 2 of their CRC study, or at any time for CGM or Reference Glucose Values less than 70 mg/dL or for symptoms of neuroglycopenia. Subjects will preselect their breakfast, lunch, and dinner meal choices from the CRC menu prior to the study. These meals will be unannounced to the FUSION system. Once the closed loop glucose control period has ended after 24 hours of glucose control, the control software will be stopped, and the subject will be disconnected from all intravenous infusions.

If the subjects are removed from the study due to the occurrence of a severe hypoglycemic event (< 54 mg/dL), the subjects will have their glucose values measured with a Reference Glucose Analyzer (e.g., Nova StatStrip Hospital Glucose Meter System) every 10 minutes, until their Reference Glucose Values are greater than 70 mg/dL. They will then have additional Reference Glucose Values drawn every 30 minutes, until they have consistent Reference Glucose Values in the range of 80-250 mg/dL for a period of at least two hours. See *Recovery Period* (Pages 107-108) for details with regards to subcutaneous insulin doses to be received prior to discharge from the Clinical Research Center.

The insulin and dextrose 50 mL medication syringes may not be used for more than 24 hours. Although the study should be terminated after a period of 24 hours (e.g., may not go longer than 24 hours), if for any reason the study period is longer than 24 hours (e.g., on orders from the principal investigator), the insulin and dextrose medication syringes must be exchanged for new medication syringes. To be clear, the insulin and dextrose medication syringes may not be used for a period of time exceeding 24 hours.

8.1.1.6 VISIT 3, TIME 29 TO 32 HOURS (OBSERVATION AFTER CLOSED LOOP GLUCOSE CONTROL SESSION)

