11.4.2 ANALYSIS OF THE PRIMARY EFFICACY ENDPOINT(S)

1. To determine percent time in range < 70 mg/dL for each subject, the calculation is as follows:

(# of glucose values in range < 70 mg/dL/total number of all glucose values) * 100

This result will be presented as median and interquartile range (25-75).

2. To determine percent time in range 70-180 mg/dL for each subject, the calculation is as follows:

(# of glucose values in range 70-180 mg/dL/total number of all glucose values) * 100

This result will be presented as median and interquartile range (25-75).

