| 19. | 
Meal Challenge Protocol
 
Time 5 hours (~1200 on day 1): Subject to consume lunch with 60 grams of carbohydrate.
 
Time 11 hours (~1800 on day 1): Subject to consume dinner with 75 grams of carbohydrate.
 
Time 25 hours (~0800 on day 2): Subject to consume breakfast with 50 grams of carbohydrate.
 
Carbohydrates should make up 45-60% of the total Kcal's of each meal.
 
Time 5 to 29 hours: Closed loop control of blood glucose with FUSION system (Figure 20), to control range of 100-140 mg/dL.
 
Throughout the entirety of the subjects stay in the CRC (e.g., time 0 to 32 hours), if the subject has a Reference Glucose Value less than 70 mg/dL or is experiencing signs of neuroglycopenia (hypoglycemia of sufficient duration and degree to interfere with normal brain metabolism and function) at any Reference Glucose Value, they will be offered snacks and/or glucose containing juice.
 |
| 20. | 
RECOVERY PERIOD (Time 29 to 32 hours)
 
1. Type 1 Diabetic Subjects:
 
Type 1 diabetic subjects will be required to have four consecutive Reference Glucose Values within the range of 80-250 mg/dL, with the most recent rate of change being less than ± 2 mg/dL/min, which is equal to either a single sideways arrow or a single up or down arrow as noted in the illustration above (Figure 29), which was taken from Dexcom G6 CGM manual.
 
The glucose sample source can be either from a venous catheter sample, or from a capillary fingerstick. The Nova StatStrip Hospital Glucose Meter System will be used to analyze the sample for glucose.
 
Following standard practice, subjects with type 1 diabetes will receive a dose of basal insulin dose two hours before discontinuation of the FUSION systems continuous insulin infusion (CII), as it is expected that basal insulin levels will slowly reach a therapeutic level after administration. An endocrinologist ([name] or [name]) will determine the dose of the basal insulin before CII discontinuation for subjects with type 1 diabetes. The next dose of basal insulin (at home) and transition to the participants home regimen will be determined by [name] or [name].
 |

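### Type 1 subjects get an investigator-set basal insulin dose at about time 27, inside the scored FUSION session, and the analysis has no rule for the readings that follow

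*Combined protocol and SAP*

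**What the plan says.** Protocol 2 (IMT2022-1-P2), item 20, covers the move off the device. For type 1 subjects it says that "subjects with type 1 diabetes will receive a dose of basal insulin dose two hours before discontinuation of the FUSION systems continuous insulin infusion". An endocrinologist sets the dose, and the same paragraph expects the basal insulin to reach a therapeutic level slowly. The instruction sits under the heading "RECOVERY PERIOD (Time 29 to 32 hours".

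The session itself is fixed in Protocol 2, item 19: "Time 5 to 29 hours: Closed loop control of blood glucose with FUSION system". Section 8.1.1.5 agrees: "Once the closed loop glucose control period has ended after 24 hours of glucose control, the control software will be stopped". The same section says that during this period "blood glucose control will be performed autonomously by Ideal Medical Technologies FUSION glucose control system".

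For both primary endpoints the Synopsis sets the window: "Time frame will be from start of use of AI controller until end of use of AI controller". Section 11.4.2 counts every value in it; the efficacy figure is the number "of glucose values in range 70-180 mg/dL/total number of all glucose values) * 100". Section 11.4.4 does the same for values below 70 mg/dL. Section 11.3 analyses everyone who begins closed loop control. Nothing in section 11 separates or flags values taken after the basal dose.

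Section 2.3 lists four controller inputs: absolute glucose, then "glucose rate of change, weight based intravenous insulin dose and weight based intravenous dextrose dose".

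For type 2 subjects, item 20 places long-acting insulin in the recovery period, after FUSION has stopped, with blanks for units and clock time. The type 1 basal dose has no such blanks.

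**The concern.** The primary objectives ask whether FUSION controls glucose safely and effectively over 24 hours. For type 1 subjects the plan schedules an insulin dose from outside the system while that question is still being scored. A low reading after the dose would be charged to FUSION alone, and a well-controlled tail would be credited to FUSION alone. The planned tables could not tell a reader that a second insulin source was present.

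The type 1 evidence is thin, which makes this worth settling in advance. The two subjects in the earlier human study had type 2 diabetes (section 2.3). Type 1 subjects were added because they lack native insulin production (Synopsis), and only two are planned (section 6.1). Sections 11.4.7 and 11.4.8 mark subgroup analysis and individual tabulation as not applicable, so the two types are pooled although only one has a dose scheduled inside the window. The affected stretch is hours 2 to 4 after the session's only breakfast, which is at time 25.

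Attribution of a safety event is also at stake. Section 9.2 counts a Reference Glucose Value below 54 mg/dL toward ending the whole study if it occurs while FUSION is in use. Such a value between time 27 and 29 would need to be read alongside the dose time.

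**Working it through.** **Inputs**
- Session: time 5 to 29 hours (section 8.1.1.5; Protocol 2, item 19).
- Basal dose: 2 hours before FUSION's insulin infusion stops (Protocol 2, item 20).
- CGM interval: 5 minutes (section 4.3.1).
- Subjects: 2 type 1 and 6 type 2 (section 6.1).
- The protocol gives no alpha, power, effect size or threshold (sections 11, 11.1 and 11.2), so there is no sample-size figure to test.

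**The plan's own figure.** 29 − 5 = 24 hours, which matches the stated session length.

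**Time of the dose.** 29 − 2 = 27 hours. With time 5 at about 1200 on day 1, this is about 1000 on day 2. It lies inside the 5–29 session and before the 29–32 period named in the heading above it.

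**Share of one affected subject's record.** 2/24 = 8.3%. At 12 readings per hour, a complete record has 24 × 12 = 288 readings, of which 2 × 12 = 24 follow the dose and 264 precede it. If the controller uses one value every 10 minutes, the counts are 12 of 144, the same 8.3%.

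**Share of the study.** If both type 1 subjects receive the dose, (2 × 24)/(8 × 288) = 48/2,304 = 2.1%. With one subject it is 24/2,304 = 1.0%; with none it is zero.

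**Effect on one subject's percentage.** Let X be the percentage over the first 22 hours and Y the percentage over the last 2. The full-session value is (22X + 2Y)/24, so it differs from X by (Y − X)/12.

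| X (first 22 h) | Y (last 2 h) | Full session | Difference from X |
|---|---|---|---|
| 100% | 0% | 91.7% | −8.3 points (ceiling) |
| 70% | 100% | 72.5% | +2.5 points |
| 80% | 100% | 81.7% | +1.7 points |
| 70% | 50% | 68.3% | −1.7 points |

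The X and Y values are assumed for illustration; the documents give none. For the safety endpoint, 30 minutes below 70 mg/dL in the last two hours and none before gives 30/1,440 = 2.1% for the session; 15 minutes gives 1.0%.

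These figures are differences between the two windows. They do not estimate what the dose causes, because the documents do not allow its effect within two hours to be calculated.

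**The case against.** The strongest reply is that little turns on this. The study is descriptive, with no hypothesis, test or decision threshold, and results are reported as a median and interquartile range over eight subjects. The post-dose readings are about 2% of the total at most. The protocol expects a slow onset, and item 9 of Protocol 2 already has visit 3 insulin doses given by a research nurse and documented in the electronic health record. All of this stands. It limits the point to a clarification and a supplementary result.

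A reader might also infer several stronger things that the documents do not support.

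- *That control after time 27 is no longer autonomous.* FUSION still sets all of its intravenous insulin and dextrose until time 29, and absolute glucose and its rate of change are among its inputs. It is not told of the dose but responds to the dose's effect. Unannounced disturbances are already part of the test: meals are unannounced (section 8.1.1.5).
- *That the first 22 hours show FUSION alone.* Evening users may take long-acting insulin the night before (section 8.1.1.3), and short-acting insulin covers the day 1 breakfast about four hours before FUSION starts (Protocol 2, item 9). Either may carry over. The time-27 dose differs in being scheduled inside the scored window, for one diabetes type only.
- *That both type 1 subjects are affected.* Item 20 has pump users restart their pumps immediately after FUSION stops and does not say whether they also receive the basal dose.
- *That a shift of about 8 points is likely.* The ceiling needs 0% in one segment and 100% in the other. For values below 70 mg/dL it needs two unbroken hours there, despite reference checks every 10 minutes (item 15) and offered snacks or juice (item 19).
- *That the type 1 primary window should end at the dose.* This would drop lows that occur while FUSION is still infusing, depart from the 24-hour objective, and pool type 1 results over 22 hours with type 2 results over 24.

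What remains is that the passages conflict and section 11 is silent on readings after the dose. A dose time in the health record does not by itself put it beside the glucose data in the report.

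**Conclusion.** The point holds as a modest but real gap. On the protocol's own times, a basal dose set by an endocrinologist falls about two hours before the end of the type 1 session, within a window described as autonomous and scored in full. Readings after it reflect FUSION plus an unannounced outside dose, and the plan neither says so nor shows the result without them.

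The size is 8.3% of an affected subject's readings, in up to two subjects, and at most about 2.1% of all study readings. The 8.3-point shift is a ceiling, and the real shift is probably much smaller given the slow onset that item 20 expects. These figures assume a full 24-hour session, complete 5-minute data and a dose given at exactly two hours before the stop. No view is taken on whether or when the basal dose should be given.

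**What to change.** 1. Keep the full-session primary and secondary endpoints as defined.
2. In sections 11.4.2 to 11.4.4, prespecify a supplementary result for each type 1 subject who receives the dose: the same glucose measures from FUSION start to the recorded time of the basal dose, shown beside the full-session value. Amend section 11.4.8, which now marks individual tabulation as not applicable, to allow this listing. State in the report that stopping at the dose does not remove carry-over from insulin given before the session.
3. Record the time of the type 1 basal dose on the case report form, with blanks in Protocol 2 like those already provided for the type 2 long-acting doses.
4. Reconcile section 8.1.1.5, the item 20 instruction and the item 20 heading, and state whether the instruction applies to pump users. The transition care stays as the investigators set it.

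The cost is one extra column, one case report form field and a few sentences. No data are lost. With two subjects at most, the supplementary figures can only describe those individuals.
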